**TEMPLATE: RESEARCH PROTOCOL**

NUMBER	ACTIVE DATE	PAGE
HRP-503	02-04-2020	6 of 35

which always have direct UC always attending coverage. All residents and attendings are ACLS/BLS/PALS trained, and all staff at the clinic are BLS trained. Additionally, the clinic is located directly adjacent to the ambulatory operating rooms and facilities, which are staffed by anesthesiologists, various other surgical specialists, nurses, nurse anesthetists, anesthesia technologists, whose resources and help are readily available if needed. Psychological outcomes do not pertain to the study. However, standard psychological resources at UC are available to any patient who receives their care at UC

**3.4 Describe your process to ensure that all persons assisting with the research are adequately informed about the protocol, the research procedures, and their duties and functions.**

A formal orientation will be held for any member involved with this study conducted by the division's research coordinator. Given that this is a blinded study certain pieces of information will be withheld from certain individuals, particularly the surgical providers, for the integrity of the research. The orientation will include presentations, and one-on-one informative meetings, as well as question and answer sessions. All members involved in the research study will be carefully monitored by the principal investigator and research coordinator for appropriate conduct and compliance with the research protocol and specific responsibilities

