**PROTOCOL:**

1.0 OBJECTIVES	1.1 Describe the purpose, specific aims, or objectives.  The goal of treatment is to re-establish the patient's preinjury dental occlusion and facial harmony. Fractures that are nondisplaced and exhibit no occlusal changes may be amenable to nonsurgical management, but most mandible fractures will require stabilization for satisfactory healing and to restore pretraumatic maxillomandibular orientation. Various treatment strategies have been described and vary widely depending on the fracture location and surgeon's preference. The patient's demographics, comorbidities, dentition, and fracture characterization will all influence the choice of fixation by the treating surgeon. [4]
	There are very few randomized control trials that show outcomes when 3D printing is used for intervention planning and performing a procedure. These data are essential to establish value of 3D printing as a clinical service. There is also anecdotal evidence that a 3D printed model of a mandible fracture can be useful for pre-operative planning because the oral and maxillofacial surgeon can better assess the geometry of the bone lesions and can pre-bend fixation plates before the procedure. This hypothetically decreases the amount of time in the operating room.
	The investigators propose a parallel design randomized control trial to study the value of 3D printing for preoperative planning in patients with a fracture of the mandible who require open reduction, internal fixation. The study will be split into two arms: 1) Patients that will

NUMBER	ACTIVE DATE	PAGE
HRP-503	02-04-2020	4 of 35

have a 3D model generated for the surgical procedure 2) The control group who will follow normal standards of care as outlined above and won't have the additional 3D model created pre-operatively.

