**1.2 Describe the hypotheses to be tested.**

The investigators will test the hypothesis that patients randomized to the intervention (3D printing with pre-bent plate) arm have less operative room time and less time for the critical part of the procedure than patients in the control arm (no 3D printing, current standards of care). Personalized medicine and care for fracture treatment.

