## TEMPLATE: RESEARCH PROTOCOL

NUMBER	ACTIVE DATE	PAGE
HRP-503	02-04-2020	5 of 35

	
3D printing is a technology that allows for physical creation of a 3D model (usually made of plastic) based on computer generated 3D images from CT scans. The 3D images of craniofacial skeleton using computer software are routinely generated and, in turn, these 3D images can be used to create a plastic 3D model using a 3D printer. Unstable or comminuted facial fractures need to be reduced and rigidly fixated using titanium plates and screws. Bending and shaping of the plates is usually performed by free hand based on the surgeon's estimation of what best fits the fracture. Often, bending the titanium plates to the shape of pre-injury skeletal contour is difficult when the bone is fractured into many pieces or is unstable, or when the patient is edentulous (missing several teeth). The process can increase the time spent in surgery and the bent plates may not snugly fit the fracture. For these difficult cases, one option is to use commercially manufactured 3D printed patient-specific models. The patient-specific models provide the benefit of correct shape/form for increased surgical accuracy and decreased intra-operative time. Thus, redefining standards of care increasing surgical satisfaction from the surgeon and patient, while decreasing the time in the OR.

	
3.1 Describe the resources available to conduct the research. Justify the feasibility of recruiting the required number of suitable subjects within the agreed recruitment period, e.g. how many potential subjects do you have access to? What percentage of those potential subjects do you need to recruit?
 
The study will be conducted at University of Cincinnati Medical Center which is designated as the region's only Level I trauma center by the American College of Surgeons. This will be a joint study with the divisions of Oral and Maxillofacial surgery, Plastics and Reconstructive surgery and Otolaryngology who are designated as the primary teams for management of all facial trauma at the institution. Thousands of consults are requested annually through UCMC ED and neighboring hospital systems for these specific injuries.

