**4.1 Detail the investigators' experience as it pertains to the study.**

**4.0 INVESTIGATOR EXPERIENCE**

[name] has been a member of the UC Surgery faculty since 2008. He is currently associate professor of surgery and is serving as the chief of OMS at UC Medical Center and Cincinnati Children's Hospital. [name] obtained his dental degree from Bangalore University, India, and trained in Oral and Maxillofacial Surgery at Emory University's College of Medicine in Atlanta, Georgia. Upon completion of residency, [name] pursued further fellowship training in Oral & Maxillofacial Surgery focusing on orthognathic surgery at Dalhousie University, Halifax, Canada. He currently serves on the Committee of Education and Training (CET) of the AAOMS and is the chair of the special committee on Emerging leaders in OMS. He is also a consultant to the AAOMS Committee on Anesthesia (CAN) on Simulation in Anesthesia. [name] was in the first class of single degree oral and maxillofacial surgeons that were recognized as Fellows of the American College of Surgeons.

[name] is Vice Chair of Operations & Quality at the University of Cincinnati Department of Radiology, and he is the clinical lead for the 3D printing section at UCH. He is the past-Chair of the American College of Radiology Appropriateness Criteria, and the Founding Chair of the Radiological Society of North America 3D Printing Special Interest Group. He also is currently the Editor-in-Chief of the journal 3D Printing in Medicine. [name] obtained his medical

	
degree through the physician scientist program at Harvard -MIT (Medicine and Medical Engineering), and he completed his residency in Diagnostic Radiology at the Brigham and Women's Hospital and Harvard Medical School, Boston, MA.

5.0 STUDY ENDPOINTS	
	
5.1 Describe any primary and secondary study endpoints.
 
Outcome 1: Noninferiority of the clinical outcome (defined by OMS on the post-op, follow up exam approx. 6 weeks out) Based on physical exam
 
Outcome 2:
 
 
Total time in the OR
 
Time in the OR considered critical part of the procedure by the OMS Staff
 
 
Outcome 3
 
 
Subjective outcome to surgeon Likert scale
 
 
5.2 Describe any primary and secondary safety endpoints.
 
Not Applicable.

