	
6.1 Thoroughly describe the study design.
 
We plan to conduct a randomized controlled trial on trauma patients brought to either UCMC or UC HH OMS for treatment of isolated mandibular fractures. This study plans to elucidate whether the utilization of 3D models during operations where effective in minimizing both OR time and operational costs. Subjects will be identified based off the initial physical assessments made by surgical specialists from OMS, Plastic Surgery, and otolaryngology. Once the subjects are identified the research coordinator will conduct a screening of the patient to ensure they meet the inclusion/ exclusion criteria for the study and then randomize the patient into either normal standard of care for surgical repair of the fractured mandible or normal standard of care for surgical repair of the fractured mandible aided by a 3D printed model of the patient's jaw. Any chart reviewing will be conducted from existing electronic medical records maintained by UC Health EPIC and OMS Vision. All the following data would be based on the patient's condition at the time of surgery.

	
Following completion of the procedure, for the surgeons who received aide via the 3D model they will be asked to answer a brief Likert Scale survey outlining their thoughts how effectively or ineffectively the model assisted them. In addition to this information, if they feel the model increased efficiency saving time, they will be asked to state how much time they felt was saved. This time differential will be compared to current CPT codes for OR time to understand how much in operational costs were saved by utilizing the models.

6.0 PROCEDURES INVOLVED	

6.2 Detail the procedures being performed, specifically the interaction or intervention with human subjects and/or their identifiable information. Please be clear and concise and provide information relevant to the current study. For
	

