**6.3 Describe procedures being performed to monitor subjects for safety or minimize risks.**

Several steps are taken to assure patient safety for surgical procedures. Prior to the procedure, their vitals are taken, including their blood pressure, heart rate, respiratory rate, and oxygen saturation. Depending on the patient, especially those with history of cardiopulmonary disease, monitors are kept cycling every five minutes during the procedure. A thorough history and physical is performed before any procedure to assure appropriate patient selection and to rule out more emergent issues. During the procedure, patients are continuously monitored with active physical examinations by the provider. There is always a certified oral and maxillofacial assistant with the patient in the room, especially during the procedure. For urgent-add on, a registered nurse is normally present as well to monitor the patient. The patient is treated via standard protocol of the oral and maxillofacial clinic at Holmes Hospital, which treats thousands of patients annually through safe, effective, and efficient measures. As explained earlier, emergency crash carts, including rescue airway carts, are present at the facility, as well as dozens of trained personnel promptly available if needed.

**6.5 Where applicable, list and describe the data collection tools such as surveys, data collection forms, etc. All tools described should be uploaded in the RAP Smart Form on the Local Site Documents page unless they are standardized, validated tools.**

Data collection will only be stored and collected on REDCap, which is a server software maintained by Cincinnati Children's Hospital Medical Center (CCHMC) informational technology team. The surgeon assigned to the case will fill out the questionnaire outlining the how effective using the 3D model was during the procedure. The outcome data will then be collected on the same secured software.

**6.6 Describe all data that will be accessed and collected during the study and how that data will be obtained (how it will be accessed).**

Description – Distinguish between data accessed and data collected if applicable.

	6.7 If there is a long-term follow-up plan (once all research related procedures are completed), what data will be collected during this period.
	No Long-Term Follow-Up

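### Section 3.4 calls the trial blinded, above all toward surgeons, yet the operating surgeon must know the allocation; critical-part time rests on what OMS staff consider critical, with no masking described

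*Protocol*

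**What the plan says.** **Blinding.** Section 3.4, on briefing study personnel, says: "Given that this is a blinded study certain pieces of information will be withheld from certain individuals, particularly the surgical providers". Blinding is mentioned nowhere else in the protocol. The section does not say what is withheld.

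**The intervention and the surgeon.** Section 1.2 tests whether patients "randomized to the intervention (3D printing with pre-bent plate) arm have less operative room time and less time for the critical part" than controls, who have no printed model. The rationale in section 1.1 is that the surgeon can study the fracture geometry on the model and "can pre-bend fixation plates before the procedure". After surgery, surgeons who had the model complete a Likert survey and, if they think it saved time, "they will be asked to state how much time they felt was saved" (section 6.1). Section 6.5 adds: "The surgeon assigned to the case will fill out the questionnaire".

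**The time outcomes.** Section 5.1 lists two under Outcome 2: total time in the operating room, and "Time in the OR considered critical part of the procedure by the OMS Staff". No start event, stop event or assessor is given for the second. Section 17.5 lists procedural time as a single item.

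**The concern.** There are two linked problems.

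First, the protocol claims a property that its design does not have. Someone who relies on section 3.4 would take the surgeons to be masked when they judge the procedure and record its outcomes. They are not.

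Second, one of the two hypothesised times depends on opinion about which part of the operation is critical. The people holding that opinion may know the arm. The intervention also changes the work at issue, because a plate shaped beforehand need not be shaped in theatre. If that step is counted in one arm and not in the other, or if the interval is opened or closed at different points, the discrepancy is added to the estimated effect and cannot afterwards be separated from it.

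**Working it through.** **Step 1: can the operating surgeon be masked to allocation?** The relevant sections, side by side:

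- Section 1.2: the intervention arm has a printed model and a pre-bent plate; the control arm has no printing.
- Section 1.1: the model serves the surgeon's own planning and plate bending.
- Section 18.7: the model is looked at ahead of surgery.
- Section 23.3 (surgeons): consent describes the questions a surgeon will answer when chosen to use the model in a given case.
- Sections 6.1 and 6.5: the surgeon on the case rates the model, and in the model arm may estimate the time it saved.

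Each of these requires the surgeon to know whether a model was used. Blinding to allocation is therefore impossible for the operator. A milder reading is that something else is withheld, such as the hypothesis. Section 3.4 does not say so, and section 23.3 has surgeons taken through the study in full at consent.

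**Step 2: is the critical-part interval fixed?** Section 5.1 ties it to what OMS staff consider critical. The protocol leaves three things open:

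- whether this is settled once for all cases or case by case;
- whether those staff are the operators, who may also come from Plastic Surgery or Otolaryngology (sections 3.1 and 10.1);
- whether they are masked.

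**Step 3: does the open boundary touch work that differs by arm?** Section 2.3 says of current practice: "Bending and shaping of the plates is usually performed by free hand", and then: "The process can increase the time spent in surgery and the bent plates may not snugly fit the fracture". Under section 1.2 the model arm has a plate bent in advance. Work on the plate therefore differs by arm, and nothing says whether it belongs to the critical part.

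Two effects must be kept apart. Time saved because bending has left the operating room is treatment effect. Bias arises only if the interval itself is drawn differently in the two arms.

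**Step 4: scale.** There is no figure in the protocol to reproduce: section 11.1 gives 50 procedures per arm and no SD for either time. As an illustration, a boundary drawn d minutes differently by arm moves the estimated mean difference by d minutes. The standard error of that difference is

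SE = SD × √(1/50 + 1/50) = 0.2 × SD.

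Take d = 5 minutes and three SDs, all assumed:

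| Assumed SD (min) | SE (min) | 5-minute shift ÷ SE |
|---|---|---|
| 20 | 0.2 × 20 = 4 | 5/4 = 1.25 |
| 30 | 0.2 × 30 = 6 | 5/6 = 0.83 |
| 45 | 0.2 × 45 = 9 | 5/9 = 0.56 |

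A larger sample shrinks the SE but leaves the 5 minutes unchanged.

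**The case against.** Section 3.4 answers a template question about orienting staff. It says that some information is kept from some people and never names allocation, so the contradiction is inferred. The sentence in section 23.3 about covering the whole study is standard wording that also appears in the patient consent text, so it is weak evidence of what surgeons learn. This has some force: the milder reading cannot be excluded. But the protocol then leaves the withheld information unexplained, and section 3.4 needs correcting on either reading.

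On the endpoint, surgeons come from three divisions but only OMS is named, which fits a single division-level definition at least as well as case-by-case judgement. Exact events might also be set out in an analysis plan or data form not at hand. Both are possible. The text states neither, and an analysis plan could not recover time stamps that were never taken.

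The protocol is also not uniform about pre-bending. Section 1.2 names a pre-bent plate, section 1.1 says only that the surgeon can bend it beforehand, and sections 6.1 and 11.1 describe the arm simply as aided by a model. How far plate work differs between arms may therefore vary by case. That does not close the boundary question.

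Three further points stand. No bias is demonstrated. Total operating room time, listed first in both 1.2 and 5.1, is untouched by the boundary argument. The two halves are separable, since fixed events would protect the time estimate even with unmasked staff. These limit the weight of the point but do not remove it. Section 17.5 does not contradict 5.1, so listing the two times separately there is a minor addition.

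**Conclusion.** The concern holds. Section 3.4 claims blinding that cannot exist for the operating surgeon if it means allocation, and is unexplained if it means anything else. Section 5.1 leaves one of the two hypothesised times to staff opinion, next to the very step that the intervention moves, with no fixed events and no masking described.

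The size of any resulting bias is unknown. The 0.56 to 1.25 standard errors shown rest on an assumed 5-minute shift and assumed SDs of 20 to 45 minutes. They indicate scale only and do not raise the importance of the point. The protocol permits a shift but does not show one. This is something the sponsor should correct: a misstated design feature and a loosely defined endpoint, both cheap to repair. Confidence is medium, because section 3.4 does not say what is withheld and section 5.1 could be read as one definition for all cases.

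**What to change.** - **Section 3.4:** state that surgeons and operating room staff are not blinded to allocation. Name anyone who is masked, and to what. If something other than allocation is withheld, say what it is.
- **Section 5.1:** replace the reference to what OMS staff consider critical with the interval between two observable events, fixed in advance, identical in both arms and time-stamped as they happen. The investigators choose the events; fracture exposure to last fixation screw is one example. This removes the boundary problem even if the people timing the case know the arm.
- **Section 17.5:** list critical-part time separately from total operating room time.

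The cost is wording in three sections and at most two extra time stamps per case. It would be fewer if the operating room record already holds them, which the protocol does not say. The one drawback is that the trial can no longer be described as blinded for surgeons.

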**3.5 Describe the facilities you have access to that will allow you to conduct the research.**

As discussed earlier, the facility that will host the research study is Holmes Hospital Oral and Maxillofacial Surgery clinic affiliated with University of Cincinnati Medical Center and the Department of Surgery

**4.1 Detail the investigators' experience as it pertains to the study.**

**4.0 INVESTIGATOR EXPERIENCE**

[name] has been a member of the UC Surgery faculty since 2008. He is currently associate professor of surgery and is serving as the chief of OMS at UC Medical Center and Cincinnati Children's Hospital. [name] obtained his dental degree from Bangalore University, India, and trained in Oral and Maxillofacial Surgery at Emory University's College of Medicine in Atlanta, Georgia. Upon completion of residency, [name] pursued further fellowship training in Oral & Maxillofacial Surgery focusing on orthognathic surgery at Dalhousie University, Halifax, Canada. He currently serves on the Committee of Education and Training (CET) of the AAOMS and is the chair of the special committee on Emerging leaders in OMS. He is also a consultant to the AAOMS Committee on Anesthesia (CAN) on Simulation in Anesthesia. [name] was in the first class of single degree oral and maxillofacial surgeons that were recognized as Fellows of the American College of Surgeons.

[name] is Vice Chair of Operations & Quality at the University of Cincinnati Department of Radiology, and he is the clinical lead for the 3D printing section at UCH. He is the past-Chair of the American College of Radiology Appropriateness Criteria, and the Founding Chair of the Radiological Society of North America 3D Printing Special Interest Group. He also is currently the Editor-in-Chief of the journal 3D Printing in Medicine. [name] obtained his medical

	
degree through the physician scientist program at Harvard -MIT (Medicine and Medical Engineering), and he completed his residency in Diagnostic Radiology at the Brigham and Women's Hospital and Harvard Medical School, Boston, MA.

5.0 STUDY ENDPOINTS	
	
5.1 Describe any primary and secondary study endpoints.
 
Outcome 1: Noninferiority of the clinical outcome (defined by OMS on the post-op, follow up exam approx. 6 weeks out) Based on physical exam
 
Outcome 2:
 
 
Total time in the OR
 
Time in the OR considered critical part of the procedure by the OMS Staff
 
 
Outcome 3
 
 
Subjective outcome to surgeon Likert scale
 
 
5.2 Describe any primary and secondary safety endpoints.
 
Not Applicable.

	
6.1 Thoroughly describe the study design.
 
We plan to conduct a randomized controlled trial on trauma patients brought to either UCMC or UC HH OMS for treatment of isolated mandibular fractures. This study plans to elucidate whether the utilization of 3D models during operations where effective in minimizing both OR time and operational costs. Subjects will be identified based off the initial physical assessments made by surgical specialists from OMS, Plastic Surgery, and otolaryngology. Once the subjects are identified the research coordinator will conduct a screening of the patient to ensure they meet the inclusion/ exclusion criteria for the study and then randomize the patient into either normal standard of care for surgical repair of the fractured mandible or normal standard of care for surgical repair of the fractured mandible aided by a 3D printed model of the patient's jaw. Any chart reviewing will be conducted from existing electronic medical records maintained by UC Health EPIC and OMS Vision. All the following data would be based on the patient's condition at the time of surgery.

	
Following completion of the procedure, for the surgeons who received aide via the 3D model they will be asked to answer a brief Likert Scale survey outlining their thoughts how effectively or ineffectively the model assisted them. In addition to this information, if they feel the model increased efficiency saving time, they will be asked to state how much time they felt was saved. This time differential will be compared to current CPT codes for OR time to understand how much in operational costs were saved by utilizing the models.

6.0 PROCEDURES INVOLVED	

6.2 Detail the procedures being performed, specifically the interaction or intervention with human subjects and/or their identifiable information. Please be clear and concise and provide information relevant to the current study. For
	

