**TEMPLATE: RESEARCH PROTOCOL**

NUMBER	ACTIVE DATE	PAGE
HRP-503	02-04-2020	12 of 35

	
of a pregnancy test are negative or until delivery.) (HRP-412 MEMBER CHECKLIST Pregnant Women)
 
 Non-Viable Neonates (HRP-413 – MEMBER CHECKLIST Non-Viable Neonates)
 
 Uncertain Viability Neonates (HRP-414 – MEMBER CHECKLIST Uncertain Viability Neonates)
 
 Prisoners (HRP-415 – MEMBER CHECKLIST Prisoners)
 
10.4 If the research involves individuals listed in 10.3 or other individuals who are vulnerable to coercion or undue influence, please justify based on the applicable checklist and describe additional safeguards included to protect their rights and welfare.
 
N/A
 
10.5 If the research involves or may involve individuals who are students or employees where the research is taking place, please describe additional safeguards included to protect their rights and welfare.
 
Not Applicable

	
11.1 Indicate the total number of subjects to be accrued.
 
We aim to obtain 50 procedures for each arm of the study (100 in total)
 
50: standard surgical procedures aided by use of 3D Printed model
 
50: procedures carried out by standard surgical repair for isolated mandibular fractures (No model)

	
11.2 If applicable, distinguish between the number of subjects who are expected to be enrolled and screened, and the number of subjects needed to complete the research procedures.
 
N/A

	
12.1 Describe when, where, and how potential subjects will be recruited.
 
Subjects of this study are those that require emergent medical attention and are referred to either UCHMS Emergency Department or to UC OMS for treatment. Subjects will be triaged by the clinical providers, and the research coordinator will then complete a standardized informative process. Regardless of involvement, the subject will undergo the same treatment course as any other patient presenting with an isolated mandibular fracture. For the consenting of the surgical team members, they will undergo a research presentation given by the research coordinator in which they have an adequate amount of time to ask any questions or concerns before deciding to be a part of the study.

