	
12.2 Describe the source of the subjects.
 
Subjects for the study are any patient are referred to HH OMS for treatment of isolated mandibular fracture. The referral arrives will need emergent medical treatment arriving from the emergency department. No subject will be sought after for the purposes of the study since the population will be emergent cases admit to UCHMC. Surgical team members will be

	
identified by both the PI and research coordinator for recruitment based off of past surgical collaboration on routine procedures at UCMC.
 
12.3 Describe the materials that will be used to recruit subjects. (Attach copies of these documents in the Recruitment section on the local site documents page in RAP. For advertisements, attach the final copy of printed advertisements (avoid making copies until approved in case modifications are required). When advertisements are taped for broadcast, attach the final audio/video tape. You may submit the wording of the advertisement prior to taping to preclude re-taping because of inappropriate wording, provided the IRB reviews the final audio/video tape)
 
N/A

13.0 COMPENSATION FOR SUBJECTS	
13.1 Describe the amount, method, and timing of payments to subjects.
 
N/A

14.0 WITHDRAWAL OF SUBJECTS	
14.1 Describe the anticipated circumstances under which subjects will be withdrawn by the study team from the research without their consent.
 
Given the strict inclusion and exclusion criteria of the study, we anticipate very few circumstances in which patients will need to withdraw by the study team without their consent.
 
14.2 Describe any procedures for orderly termination.
 
Patients will be withdrawn from the study if they unfortunately succumb to their injuries related to any polytrauma that caused the underlying mandibular fracture before any procedures can be completed. Surgeons who no longer wish to provide feedback via the Likert scale questions will also no longer be associated with the study.
 
14.3 Describe procedures that will be followed when subjects withdraw from the research, including partial withdrawal from procedures with continued data collection, withdrawal of previously collected data upon request, etc.
 
Patients and surgeons who are withdrawn from the study for the purposes listed earlier will be excluded from all study results.

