
17.0 DATA MANAGEMENT AND CONFIDENTIALITY
	
17.1 Describe the data analysis plan, including any statistical procedures or power analyses.
 
We are going to use the Likert questions to develop a numerical scoring system and report that data as “raw” Likert scores. Likert questions and conversion of specialists’ responses to Anatomic Model Utility Points (AMUPs). Responses of “strongly disagree”, “disagree”, and “neutral” were assigned 0 AMUP points. Responses to preprocedural confidence are assigned negative points, to effectively subtract the impact of the anatomic model post- versus pre-procedure. The maximum AMUP for each patient was 500.

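### Outcome 1 claims noninferiority at six weeks with no margin, outcome definition or power basis, so the protocol gives no valid rule for concluding it

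*Protocol*

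**What the plan says.** Section 5.1 gives three numbered outcomes and calls none of them primary. The first is "Noninferiority of the clinical outcome", to be defined by the oral and maxillofacial surgeons from a physical exam about six weeks after surgery. The second is time in the OR, in total and for the critical part. The third is a surgeon Likert score. Section 5.2 answers that safety endpoints do not apply.

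The hypothesis in 1.2 is that the 3D-printing arm has "less operative room time and less time for the critical part of the procedure". Noninferiority does not appear there.

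On size, 11.1 says "We aim to obtain 50 procedures for each arm of the study (100 in total" and gives no derivation. Section 11.2, where the template asks for "the number of subjects needed to complete the research procedures", is answered as not applicable. In 17.1 the template prompt is "Describe the data analysis plan, including any statistical procedures or power analyses"; the answer describes only the scoring of Likert responses.

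Four other places bear on whether a six-week result will exist for every patient:
- 9.1 limits participation to a single appointment.
- 18.1 ends participation with the procedure, although 18.4 refers to a standard six-week follow-up.
- 17.5 lists the data as procedure time, cost difference and Likert answers, without the six-week exam.
- 14.3 says withdrawn patients and surgeons "will be excluded from all study results".

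**The concern.** Noninferiority has meaning only against a margin fixed in advance. Without one, nothing in the protocol says which result would count as noninferior. Two substitutes then become available, and neither is evidence: a margin picked once the data are known, or a non-significant difference read as equivalence.

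The second is easy to illustrate. With 5 poor results among 50 in each arm, the observed difference is zero, yet the upper limit of the Newcombe 95% interval is 12.7 points.

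The stakes are real because, with 5.2 answered as not applicable, Outcome 1 is the only listed endpoint that concerns how the patient fares. A noninferiority statement would be read as assurance that time saved in the OR costs nothing clinically.

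**Working it through.** **The plan's own figure.** The 50 per arm cannot be reproduced. The protocol gives no alpha, power, margin, event rate, standard deviation or effect size. The check therefore runs in reverse: which margin can 50 per arm support?

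**Inputs.** From the protocol: n = 50 per arm (11.1). Assumed, because the protocol does not state them: a binary poor-outcome endpoint, equal true rates p in both arms, one-sided alpha 2.5%, power 80%, and no loss of patients. The last assumption favours the protocol.

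**Formulas.** k = 1.960 + 0.8416 = 2.8016, so k² = 7.849.
- SE = √(2p(1−p)/50)
- Smallest margin with 80% power: m = k × SE
- Power at a 10-point margin: Φ(0.10/SE − 1.96)
- n per arm for a 10-point margin at 80% power: k² × 2p(1−p)/0.10²

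Example at p = 10%: SE = √(0.18/50) = 0.060; m = 2.8016 × 0.060 = 0.168; allowed rate 10% + 16.8% = 26.8%, or 2.7 times control.

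| Control rate (assumed) | SE | Margin, points | Allowed rate | Ratio to control | Power at 10 points | n per arm for 10 points |
|---|---|---|---|---|---|---|
| 5% | 0.0436 | 12.2 | 17.2% | 3.4 | 63.1% | 75 |
| 10% | 0.0600 | 16.8 | 26.8% | 2.7 | 38.5% | 142 |
| 15% | 0.0714 | 20.0 | 35.0% | 2.3 | 28.8% | 201 |
| 20% | 0.0800 | 22.4 | 42.4% | 2.1 | 23.9% | 252 |
| 25% | 0.0866 | 24.3 | 49.3% | 1.97 | 21.0% | 295 |
| 40% | 0.0980 | 27.4 | 67.4% | 1.69 | 17.4% | 377 |

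**Where doubling stops.** Setting m = p gives p = 2k²/(50 + 2k²) = 15.70/65.70 = 23.9%. Below that rate the supportable margin more than doubles the control rate; above it, it does not. The threshold moves to 29.6% at 90% power, and to 19.8% (80% power) or 25.5% (90% power) at one-sided 5%.

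**Exact check.** Exact binomial power with the Newcombe interval, in half-point steps, gives margins of 14.5, 18.0, 20.5, 22.5 and 24.0 points at 5%, 10%, 15%, 20% and 25%. The ratios are 3.9, 2.8, 2.4, 2.1 and 1.96, so the picture is the same.

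**If the model truly helps.** With true rates of 15% (control) and 10% (model), m = 2.8016 × √(0.1275/50 + 0.09/50) − 0.05 = 0.135, a ratio of 1.9.

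**If the outcome is continuous.** m = 2.8016 × √(2/50) = 0.56 SD at 80% power, and 0.65 SD at 90%.

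**The case against.** The strongest reply has three parts.

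First, margins are often set in a statistical analysis plan, which may exist here. This is partly right. A margin fixed there before any outcome data are seen would supply the decision rule. But the protocol itself chose both the claim and the 50 per arm, and no later document changes what that number can support.

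Second, a reader might infer from the table that 50 per arm can meet only margins that let complications double. The documents do not support this.
- The protocol speaks of a clinical outcome "Based on physical exam". It does not call it complications or say that it is binary. Section 6.2 names occlusion and facial form as the treatment goals, and these could be scored on a scale, where doubling has no meaning.
- The doubling also needs a control rate below about 24% and no true difference between arms.
- Margins with 80% power are not the only ones that can be met. At equal rates of 20%, a margin of 1.96 × 0.08 = 15.7 points, which allows 1.8 times the control rate, would be met about half the time.

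Third, nothing shows that the 50 per arm was meant to size Outcome 1. The numbering in 5.1 is not a stated hierarchy, and 1.2 points to OR time as the trial's question. This stands, and it supports taking the noninferiority wording out rather than enlarging the trial. Nor does any passage say that a non-significant difference will be reported as noninferior. That is a risk the text leaves open, not a stated plan.

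**Conclusion.** The point holds in a limited form. On the protocol's text, Outcome 1 asserts noninferiority with no margin, no definition of the outcome and no power basis, and the stated hypothesis does not include it. There is no valid rule for reaching the conclusion that the outcome names.

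The size is conditional. For a binary outcome with equal true rates of 5% to 20%, one-sided 2.5%, 80% power and no losses, 50 per arm supports margins of about 12 to 22 points, and the allowed rate is 3.4 down to 2.1 times control. The more-than-double description ends at a control rate of about 24%, although the margin in points keeps growing (27.4 at 40%). For a continuous outcome the figure is 0.56 SD. Whether any of these margins is clinically acceptable is for the sponsor to argue, and the protocol does not do so.

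Apart from the arithmetic, the sections on participation, data collection and withdrawal do not agree with a six-week comparison of all randomised patients.

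**What to change.** In 5.1, name OR time, the hypothesis in 1.2, as the primary outcome, and say which of its two times leads or how both are handled. Restate Outcome 1 as a defined secondary clinical outcome, reported as the difference between arms with its 95% CI in all randomised patients, and remove the word noninferiority.

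If the claim is to stay, define the outcome, fix and justify the margin before any outcome data are seen, and state the power that 50 per arm gives for it.

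Either way, reconcile four other sections: add the six-week exam to the data list in 17.5; make 9.1 and 18.1 agree with a six-week assessment; and revise 14.3, whose exclusion of withdrawn patients conflicts with analysing everyone randomised.

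The cost is a less favourable claim and small wording changes in these sections. Dropping the claim needs no extra patients. Keeping it with a 10-point margin at 80% power would need 75 to 252 per arm for assumed rates of 5% to 20%.
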